9.4.5 Baseline Descriptive Statistics

Baseline characteristics will be summarized by treatment arm. For continuous measures the mean and standard deviation will be summarized. Categorical variables will be described by the proportion in each category (with the corresponding sample size numbers).

9.4.6 Planned Interim and Early Analyses

A DSMB will monitor ongoing results to ensure subject well-being and safety as well as study integrity. The DSMB will be asked to recommend early termination or modification only when there is clear and substantial evidence of a treatment difference. More details about the interim analyses are described in [section 9.4.6.1](#) and [9.4.6.2](#) below as well as a separate guidance document for the DSMB.

9.4.6.1 Interim Safety Analyses

Safety analyses will evaluate Grade 3 and 4 AE and SAEs by treatment arm. Safety monitoring will be ongoing (see [section 10.1.6](#)). The unblinded statistical team will prepare these reports for review by the DSMB.

9.4.6.2 Interim Efficacy Review

The Lan-DeMets spending function analog of the O'Brien-Fleming boundaries will be used to monitor the primary endpoint as a guide for the DSMB for an overall two-sided type-I error rate of 0.05. Interim efficacy analyses will be conducted at approximately 33%, and 100% of total information.

Conditional power will be presented as an additional guide to the DSMB. Conditional power allows computation of the probability of obtaining a statistically significant result by the end of the trial given the data accumulated thus far, incorporating and assuming a hypothesized treatment effect (e.g., the treatment effect assumed for sample size determination) thereafter. If conditional power is less than 20% under the original trial assumptions, consideration should be given to stopping the trial.

The unblinded statistical team will prepare these closed reports for DSMB review and recommendations. Analyses will be presented with blinded codes for treatment arms to protect against the possibility that the DSMB report may fall into the wrong hands. A DSMB charter will further describe procedures and membership. An additional document on statistical issues related to monitoring will be provided to the DSMB prior to interim analyses.

9.4.7 Sub-Group Analyses

Subgroup analyses for the primary outcomes will evaluate the treatment effect across the following subgroups: geographic region, duration of symptoms prior to enrollment, baseline disease severity (stratification variable of mild/moderate and severe, as well as ordinal scale of 4/5 vs 6/7) age, race, sex and comorbidities. A forest plot will display confidence intervals across subgroups. Interaction tests will be conducted to determine whether the effect of treatment varies by subgroup.

9.4.8 Exploratory Analyses

An exploratory analysis will compare treatment efficacy estimates according to the various scales outlined in [section 8.1.2](#). Specifically, the probability of falling into category “i” or better will be compared between arms for each i.

10. SUPPORTING DOCUMENTATION AND OPERATIONAL CONSIDERATIONS – ALL STAGES

All supporting documentation and operational considerations are applicable to the entire platform trial and are not unique to the individual stages. These are therefore covered in the main protocol document.

APPENDIX C - ACTT-3: REMDESIVIR + INTERFERON BETA-1A

1. PROTOCOL SUMMARY

1.1 ACTT-3 – Synopsis

Study overview

ACTT-3 will evaluate the combination of subcutaneous interferon beta-1a and remdesivir compared to placebo and remdesivir. In vitro studies suggest significant suppression of the intrinsic interferon response following SARS-CoV-2 infection. (1-6) Recent data from several studies indicate that there may be a subset of hospitalized patients with COVID-19 who lack a prominent interferon signature despite high viral titers and this phenotype may be associated with worse clinical outcomes (14-17). Type 1 interferon can inhibit SARS-CoV, MERS-CoV, and SARS-CoV-2 in vitro (18-21) and recent data suggests that SARS-CoV-2 may be more sensitive than SARS-CoV to inhibition by interferon (18, 22). Lastly, two small RCTs and an exploratory, non-randomized clinical trial in hospitalized adult COVID-19 patients suggest a possible clinical benefit from treatment with interferon beta (23-25). In summary, there is emerging data that suggests interferon may be a good candidate to improve outcomes of patients with COVID-19.

Enrollment Period

It is anticipated that enrollment may be completed in 3 to 4 months.

General

The design of ACTT-3 will follow the design of ACTT-1 and ACTT-2. Subjects will be assessed daily while hospitalized. If the subjects are discharged from the hospital, they will have a study visit at Days 15, 22, and 29. For discharged subjects, it is preferred that the Day 15 and 29 visits are in person to obtain safety laboratory tests and OP swab and blood (serum only) samples for secondary research as well as clinical outcome data. However, infection control or other restrictions may limit the ability of the subject to return to the clinic. In this case, these visits may be conducted by phone, home visit or remote telehealth procedure as per institutional standards. If Day 15 and 29 visits are conducted by phone or remotely by telehealth procedure, only clinical data will be obtained (i.e., no specimens). The Day 22 visit does not have laboratory tests or collection of samples and is conducted by phone or remote telehealth procedure.

The trial will enroll only those subjects with mild moderate disease (defined as being in ordinal category 4 and 5). The trial initially enrolled ordinal category 6 (those on high flow oxygen or non-invasive mechanical ventilation), but enrollment in this category was closed September 4, 2020 after the DSMB reviewed interim safety data and noted concern for risk in this category. Emerging data from ACTT-1 (remdesivir vs placebo) (26) and the RECOVERY trial (dexamethasone vs standard of care) (27) suggests that the hospitalized population may be a continuum where control of the virus is most important in mild disease and control of the host inflammatory response is most important late in the disease. Interferon, having antiviral as well - and anti-inflammatory properties, may have increased the inflammation seen in those enrolled as ordinal category 6. Therefore neither ordinal category 6 or 7 (those on mechanical ventilation or ECMO) will be enrolled in this trial. The DSMB confirmed that there was no signal or concern for harm in ordinal 4 or 5 categories, and they recommended the study continue to enroll patients in those groups.

The trial will accrue until approximately 831 recoveries. Assuming that 90% of subjects achieve recovery in 28 days, the total sample size is approximately 923.

Study Population

Hospitalized adults (≥ 18 years old) with COVID-19.

Inclusion Criteria

1. Admitted to a hospital with symptoms suggestive of COVID-19.
2. Subject (or legally authorized representative) provides informed consent prior to initiation of any study procedures.
3. Subject (or legally authorized representative) understands and agrees to comply with planned study procedures.
4. Male or non-pregnant female adults ≥ 18 years of age at time of enrollment.
5. Has laboratory-confirmed SARS-CoV-2 infection as determined by PCR or other commercial or public health assay (e.g., NAAT and antigen tests) in any respiratory specimen or saliva, as documented by either of the following:
 - PCR or other assay positive in sample collected < 72 hours prior to randomization; OR
 - PCR or other assay positive in sample collected ≥ 72 hours but < 7 days prior to randomization AND progressive disease suggestive of ongoing SARS-CoV-2 infection.
- Note: if written documentation of the positive test result is not available at the time of enrollment (e.g., report came from other institution), the subject may be enrolled but the PCR should be repeated at the time of enrollment.*
6. Illness of any duration, and at least one of the following:
 - Radiographic infiltrates by imaging (chest x-ray, CT scan, etc.), OR
 - $\text{SpO}_2 \leq 94\%$ on room air, OR
 - Requiring supplemental oxygen
7. Women of childbearing potential must agree to either abstinence or use at least one primary form of contraception not including hormonal contraception from the time of screening through Day 29.
8. Agrees to not participate in another clinical trial (both pharmacologic and other types of interventions) for the treatment of COVID-19 through Day 29.

Exclusion Criteria

1. Anticipated discharge from the hospital or transfer to another hospital which is not a study site within 72 hours.
2. Subject meets criteria for ordinal scale category 6 or 7 at the time of screening.
3. Subject has a positive test for influenza virus during this current hospital admission
4. Subjects with an estimated glomerular filtration rate (eGFR) < 30 mL/min are excluded unless in the opinion of the PI, the potential benefit of receiving remdesivir outweighs the potential risk of study participation.
5. ALT or AST > 5 times the upper limits of normal.
6. Total white cell blood cell count (WBC) < 1500 cells/ μL .

7. Platelet count <50,000/ μ L.
8. History of chronic liver disease (e.g., jaundice, ascites, hepatic encephalopathy, history of bleeding esophageal or gastric varices). No laboratory testing is needed.
9. Pregnancy or breast feeding (lactating women who agree to discard breast milk from Day 1 to three weeks after the last study product is given are not excluded).
10. Allergy to any study medication including history of hypersensitivity to natural or recombinant interferon beta or human albumin.
11. Patient has a chronic or acute medical condition or is taking a medication that cannot be discontinued at enrollment, that in the judgement of the PI, places them at unacceptable risk for a poor clinical outcome if they were to participate in the study.
12. Received three or more doses of remdesivir, including the loading dose, outside of the study for COVID-19.
13. Received convalescent plasma or intravenous immunoglobulin [IVIg] for the treatment of COVID-19.
14. Received any interferon product within two weeks of screening, either for the treatment of COVID-19 or for a chronic medical condition (e.g., multiple sclerosis, HCV infection).
15. Received any of the following in the two weeks prior to screening as treatment of COVID-19:
 - small molecule tyrosine kinase inhibitors (e.g., baricitinib, imatinib, gefitinib, acalabrutinib, etc.);
 - monoclonal antibodies targeting cytokines (e.g., TNF inhibitors, anti-interleukin-1 [IL-1], anti-IL-6 [tocilizumab or sarilumab], etc.);
 - monoclonal antibodies targeting T-cells or B-cells as treatment for COVID-19.
16. Prior enrollment in ACTT-3

Study Intervention

Subjects will be randomized into two arms (1:1).

Arm 1	Arm 2
Interferon beta-1a SQ injection + remdesivir IV	Placebo SQ injection + remdesivir IV

All subjects will receive remdesivir as a 200 mg intravenous (IV) loading dose on Day 1, followed by a 100 mg once-daily IV maintenance dose during hospitalization up to a maximum of 10 total doses (i.e., loading + maintenance doses received during study and pre-study if applicable). The duration of dosing may be adjusted by the site similar to what is described in the emergency use authorization and based on a subject's clinical course and ultimate disease severity.

For the subcutaneous interferon beta-1a or placebo component, subjects will receive either active product or placebo as follows:

- Interferon beta-1a will be administered every other day as a 44-microgram subcutaneous dose for a total of 4 doses while hospitalized.

- A matching placebo will be administered every other day as a subcutaneous injection for a total of 4 doses while hospitalized.

Duration of therapy:

- IV remdesivir – 5 - 10 consecutive days while hospitalized. A full 10-day course in patients still in the hospital is not required per protocol.
- Subcutaneous (interferon beta-1a or placebo) component – Days 1, 3, 5, and 7 while hospitalized.
- Both stop on discharge from hospital. If readmitted after discharge, see [Section 7.4](#).

1.2 Schedule of Assessments

Table 1. Schedule of Assessments (SOA)

	Screen	Baseline	Study Intervention Period	Follow-up Visits		
Day +/- Window	-1 or 1	1	Daily until hospital discharge	15⁷ ± 2	22⁷ ± 3	29⁷ + 6
ELIGIBILITY						
Informed consent	X					
Demographics & Medical Hx	X					
Review SARS-CoV-2 results	X					
STUDY INTERVENTION						
Randomization		X				
Administration of investigational agent			
 • Remdesivir daily infusion for 5-10 days or until discharge. • Interferon beta-1a or placebo SQ injection on Days 1, 3, 5, and 7, or until discharge. 			
STUDY PROCEDURES						
Targeted physical exam		X				
Vital signs including SpO ₂ ¹		X ⁴	Daily until discharge ⁸	X ⁹		X ⁹
Clinical data collection ²		X ⁴	Daily until discharge ⁸	X ⁹	X ⁹	X ⁹
Adverse event evaluation		X ⁴	Daily until discharge ⁸	X ⁹	X ⁹	X ⁹
Concomitant medication review	X	X	From Day -7 to Day 29			
SAFETY LABORATORY						
Safety hematology, chemistry and liver tests	X ³	X ^{4,5,6,7}	Day 3, 5, 8, 11 (all ± 1 day) if hospitalized ^{6,7}	X ⁹		X ⁹
Pregnancy test for females of childbearing potential	X ³					
RESEARCH LABORATORY FOR ALL SUBJECTS						
Blood for plasma to test by PCR for SARS-CoV-2 and cytokines/inflammatory markers		X ⁴	Day 3, 5, 8, 11 (all ± 1 day) if hospitalized			X ⁹

Oropharyngeal swab ¹⁰		X ⁴	Day 3, 5, 8, 11 (all ± 1 day) if hospitalized	X ⁹		X ⁹
Blood for serum (secondary research)		X ⁴	Day 3, 5, 8, 11 (all ± 1 day) if hospitalized	X ⁹		X ⁹
ONLY FOR SUBJECTS CONSENTING FOR GENETIC RESEARCH						
Blood for RNA for transcriptomic analysis (in PAXgene tube)		X ⁴	Day 3, 8 (all ± 1 day) if hospitalized	X ^{9, 11}		X ⁹
Blood for PBMC to T cells/innate cells and epigenetics (in CPT) ¹²		X ^{4,12}	Day 8 (all ± 1 day) if hospitalized ¹²	X ^{9, 11, 12}		X ^{9, 12}

Notes:

¹Vital signs include temperature, systolic blood pressure, heart rate, respiratory rate, O₂ saturation and level of consciousness. Vital signs collected as part of standard care may be used.

²Refer to [Section 8.1.2](#) of the protocol for details of clinical data to be collected including ordinal score, NEWS, oxygen requirement, mechanical ventilator requirement, etc.

³Screening laboratory tests include: white blood cell (WBC) count, platelet count, ALT, AST, and creatinine (and calculate an estimated glomerular filtration rate (eGFR) the formula used is determined by the sites, but should be consistent throughout the study), and pregnancy test. Laboratory tests performed in the 48 hours prior to enrollment will be accepted for determination of eligibility. See [Section 8.1.1](#) for more information about pregnancy tests in post-partum women.

⁴Baseline assessments should be performed prior to first study product administration. Results of Day 1 (baseline) laboratory assessment do not need to be reviewed to determine if initial study product should be given.

⁵Laboratory tests performed as part of routine clinical care in the 36 hours prior to first dose will be accepted for the baseline safety laboratory tests. Baseline may be the same as the screening laboratory tests.

⁶Safety laboratory tests include WBC count, differential, hemoglobin, platelet count, creatinine, total bilirubin, ALT, AST, INR, d-dimer, and C-reactive protein (CRP). Note: D-dimer and CRP values may predict severity and support assessment of outcomes and unlike other safety laboratory values, D-dimer and CRP should not be graded.

⁷Any laboratory tests performed as part of routine clinical care within the specified visit window can be used for safety laboratory testing.

⁸Daily until hospital discharge or end of study, whichever comes first. See [Section 8.1.2.1](#) for more information about doing an ordinal scale assessment on the day after hospital discharge and on the day after a subject dies.

⁹In-person visits are preferred but recognizing quarantine and other factors may limit the subject's ability to return to the site for the visit. In this case, the visit may be performed by phone call, home visit or remote telehealth procedure as per institutional standards. If subject is still hospitalized during the follow-up period, they should get Day 15, 22 and 29 assessments along with the daily clinical data collection.

- If still hospitalized at Day 15 and 29 or returns to the site for an in-person visit or home visit: collect clinical data, vital signs, safety laboratory tests, and research laboratory samples (OP swab and serum only) as able.
- If phone call or remote telehealth visit only on Days 15 and 29 and all Day 22 visits: assess adverse events, clinical status (ordinal scale), readmission to a hospital, and mortality only.

¹⁰Oropharyngeal swabs are preferred, but if these are not obtainable, nasopharyngeal or nasal swabs may be substituted.

¹¹Subjects who consented for genetic testing and are discharged prior to Day 8 (or Day 11 for proteomics) should get blood drawn at Day 15. That is, if subject is missing either a Day 8 Paxgene or CPT sample, or Day 11 proteomic sample, get missing sample (proteomics, PAXgene or PBMC) at the Day 15 visit if site is able to do an in-person visit.

¹²Only collected at selected clinical trial sites that are capable of collecting and processing PBMCs.

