To evaluate the clinical efficacy of RDV+ interferon beta-1a compared to RDV + placebo, as assessed by time to recovery for patients with a baseline ordinal score of 4 and 5.	
Day of recovery is defined as the first day on which the subject satisfies one of the following three categories from the ordinal scale:
 
 • Hospitalized, but not requiring supplemental oxygen and– no longer requires ongoing medical care; • Not hospitalized, but new or increased limitations on activities and/or new or increased requirement for home oxygen; • Not hospitalized, no limitations on activities. 
Recovery is evaluated up until Day 29 (+ 6 days).

Additional Secondary- by baseline severity moderate (4 or 5) and severe (6)	

To evaluate the clinical efficacy of RDV+ interferon beta-1a compared to RDV + placebo as assessed by:
 
 • Clinical Severity 
 ○ Ordinal scale: 
 ▪ Time to an improvement of one category and two categories from Day 1 (baseline) using an ordinal scale. 	
 • Clinical outcome assessed using ordinal scale daily while hospitalized and on Days 15, 22, and 29.

OBJECTIVES	ENDPOINTS (OUTCOME MEASURES)

 ▪ Subject clinical status using ordinal scale at Days 3, 5, 8, 11, 15, 22, and 29. ▪ Mean change in the ordinal scale from Day 1 to Days 3, 5, 8, 11, 15, 22, and 29. 	

 ○ National Early Warning Score (NEWS): 
 ▪ Time to discharge or to a NEWS of ≤ 2 and maintained for 24 hours, whichever occurs first. ▪ Change from Day 1 to Days 3, 5, 8, 11, 15, and 29 in NEWS. 	
 ● NEWS assessed daily while hospitalized and on Days 15 and 29.

 ○ Oxygenation: 
 ▪ Oxygenation use up to Day 29. ▪ Incidence and duration of new oxygen use during the study. 	
 ● Days of supplemental oxygen (if applicable) up to Day 29

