3.3.8. Days of Oxygen

Oxygen days will be defined as the number of days where the clinical status score is equal to 5, 6, or 7. The Post-Discharge Supplemental Oxygen CRF question regarding days of oxygenation (including ECMO, invasive ventilation, non-invasive ventilation, high-flow oxygen devices, and all other oxygen delivery devices) will be used for any time period the subject is not hospitalized at the study hospital. The total number of days will be the sum of all reported days, regardless of whether the days occur consecutively or in disjoint intervals. See Section 6.5 for the plan for handling subjects who do not have data through Day 29 or die prior to Day 29.

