The original (as-classified by the site) ordinal scores will be used as the primary scoring method for analyses. The following modified ordinal scale will be used in sensitivity analysis of select outcomes:

8. Death;
7. Hospitalized, on invasive mechanical ventilation or ECMO;
6. Hospitalized, on non-invasive ventilation or high flow oxygen devices at oxygen flow rate greater than 15L/min;
5. Hospitalized, requiring supplemental oxygen or high flow oxygen devices at oxygen flow rate less than or equal to 15L/min;
4. Hospitalized, not requiring supplemental oxygen - requiring ongoing medical care (COVID-19 related or otherwise);
3. Hospitalized, not requiring supplemental oxygen - no longer requiring ongoing medical care;
2. Not hospitalized, but new or increased limitation on activities and/or requiring new or increased home oxygen;
1. Not hospitalized, no limitations on activities.

This scale will be denoted as the “Modified Oxygen Use” ordinal scale.

NEWS has demonstrated an ability to discriminate subjects at risk of poor outcomes. This score is based on 7 clinical parameters (see Section 8.1.2.3 in Appendix C of the study protocol). This should be evaluated at the first assessment of a given study day and prior to administration of study product. The 7 parameters can be obtained from the hospital chart using the last measurement prior to the time of assessment and a numeric score given for each parameter (e.g., a RR of 9 is one point, oxygen saturation of 92 is two points). This is recorded for the day obtained. i.e., on Day N, the Day N score is obtained and recorded as the Day N score.

Oxygenation, Non-invasive ventilation/high flow oxygen, Invasive Mechanical Ventilation / extracorporeal membrane oxygenation (ECMO), hospitalization and mortality will be assessed using results of the 8-point ordinal scale and post discharge eCRF questions.

Safety will be assessed by the following:

- Cumulative incidence of serious adverse events (SAEs) through 28 days of follow-up.
- Cumulative incidence of Grade 3 and 4 AEs.
- Discontinuation or temporary suspension of study product administration (for any reason).
- Changes in white cell count, hemoglobin, platelets, creatinine, total bilirubin, ALT, AST, and INR, d-dimer, C-reactive protein over time. Note D-dimer and CRP are not graded.

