 - If the subject is discharged (not to hospice or other end-of-life care) prior to the missing study day, a NEWS score of 2 will be imputed.
 - If the subject is neither dead nor discharged, use the previous NEWS total score, or missing component-carried forward for all subsequent visits.
- Days of Non-invasive ventilation/high-flow oxygen:
 - If the subject's clinical status scale is 6 at the last observed assessment, then the subject will be considered to be on non-invasive ventilation/high-flow oxygen through Day 29. The endpoint will be total days when assessments are available plus all imputed days following the last observed assessment.
 - If the subject is not on non-invasive ventilation/high-flow oxygen at the last observed assessment, then the subject will be considered to not be on non- invasive ventilation/high-flow oxygen for the remainder of follow-up. Thus, no additional imputed days will be added to the number of days recorded on available assessments.
- Days of ventilation/ECMO:
 - If the subject's clinical status scale is 7 at the last observed assessment, then the subject will be considered to be on ventilation/ECMO through Day 29. The endpoint will be total days when assessments are available plus all imputed days following the last observed assessment.
 - If the subject is not on ventilation/ECMO at the last observed assessment, then the subject will be considered to not be on ventilation/ECMO through Day 29. Thus, no additional imputed days will be added to the number of days recorded on available assessments.
- Days of Oxygen:
 - If the subject's clinical status score is 5, 6, or 7 at the last observed assessment, then the subject will be considered to be on oxygen through Day 29. The endpoint will be total days when assessments are available plus all imputed days following the last observed assessment.

- If the subject is not on oxygen at the last observed assessment, then the subject will be considered to not be on oxygen through Day 29. Thus, no additional imputed days will be added to the number of days recorded on available assessments.
- Days of Hospitalization
 - If the subject is discharged and no further hospitalization data are available, then the subject will be assumed to not have been readmitted. Thus, no additional imputed days will be added to the number of days recorded on available assessments. If a subject dies while hospitalized, the number of days of hospitalization will be imputed as 28 days.

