8.2.4. Incidence of New Oxygen use

The incidence and duration of new oxygen use will be analyzed by treatment arm. This will only include subjects in category 4 at randomization. New use will be identified by a post-randomization score of at least 5; the number of subjects reporting new use and the incidence rate (and CI) will be reported.

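### The SAP takes out-of-hospital oxygen days from a post-discharge CRF that the protocol's remote-visit list omits, and its imputation and new-use rules have no place for home oxygen

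*Protocol*

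**What the plan says.** **Endpoint.** Protocol Appendix C section 3 lists, among the additional secondary endpoints, "Days of supplemental oxygen (if applicable) up to Day 29". It has matching entries for non-invasive ventilation/high-flow oxygen and for invasive ventilation/ECMO.

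**Counting rule.** SAP 3.3.8 has two sources. While the patient is in the study hospital, "Oxygen days will be defined as the number of days where the clinical status score is equal to 5, 6, or 7". Otherwise, the question on the Post-Discharge Supplemental Oxygen CRF "will be used for any time period the subject is not hospitalized at the study hospital". That question covers ECMO, ventilation and high-flow devices "and all other oxygen delivery devices", so home oxygen is included. SAP 3.3.6 and 3.3.7 use the same CRF for their own endpoints. SAP 4.3 confirms that these outcomes "will be assessed using results of the 8-point ordinal scale and post discharge eCRF questions".

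**Visit content.** Footnote 9 of the Appendix C Schedule of Assessments restricts phone and telehealth contacts on Days 15 and 29, and every Day 22 visit. Sites are to "assess adverse events, clinical status (ordinal scale), readmission to a hospital, and mortality only".

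**Missing data.** SAP 6.5 applies to patients lost to follow-up, terminated early, or without further outcome data after discharge. Its carry-forward condition is worded by score: "clinical status score is 5, 6, or 7 at the last observed assessment, then the subject will be considered to be on oxygen". All days left up to Day 29 are then added. If the subject is not on oxygen at that assessment, none are added.

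**New use.** SAP 8.2.4 considers patients in category 4 at randomization: "New use will be identified by a post-randomization score of at least 5".

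**The concern.** The protocol's list of what to ask at remote contacts does not contain the item that the SAP needs for every day spent away from the study hospital. The ordinal score cannot stand in for it. Under Appendix C 8.1.2.2, a follow-up score describes only the previous calendar day. Score 2 also pools activity limitation with new or increased home oxygen.

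Two SAP rules then fall back on scores of 5 or more, which a patient at home cannot have. Capture could therefore depend on whether a visit was held in person or by phone, and on where the patient was when oxygen was used.

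The primary endpoint counts discharge at score 2, home oxygen included, as recovery. Days of oxygen is the secondary outcome that could show whether earlier recovery reflected less oxygen or only oxygen continued at home. It is least secure for those patients.

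**Working it through.** The documents give no figure for oxygen days, home-oxygen use or the share of remote visits, so there is no plan figure to reproduce. The check applies the SAP rules to cases and then shows a range under stated assumptions.

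**1. Worked patient (assumed).** Oxygen on all 28 days: 7 in hospital at score 5, then 21 at home at score 2.

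Counted days = in-hospital days at scores 5 to 7 + CRF-reported days + days imputed under SAP 6.5.

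| Situation | In hospital | CRF | Imputed | Count |
|---|---|---|---|---|
| CRF answered | 7 | 21 | 0 | 28 |
| CRF unanswered, 6.5 applied by score alone | 7 | 0 | 0 | 7 |
| Same patient terminates early in hospital at score 5 | 7 | 0 | 21 | 28 |

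With 5, 10 or 14 in-hospital days, the middle row gives 5, 10 or 14, a loss of 23, 18 or 14 days. The first and third rows stay at 28.

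The middle row depends on how SAP 6.5 is programmed. A patient last seen at score 2 on home oxygen does not meet the 5-to-7 condition, yet is not literally off oxygen either. The text has no branch for this patient, and a program that uses scores alone would add no days.

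**2. New use, with the CRF complete.** Take a category-4 patient who goes home and first uses oxygen there. The score never reaches 5, so SAP 8.2.4 does not record a case. SAP 3.3.8 counts the same days as oxygen days. The programming note to SAP Table 33 limits the days summary for patients not on oxygen at baseline to those who reported new use. If that follows 8.2.4, the days drop out there too.

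**3. Possible distortion between arms.** Let d be the between-arm difference in the share discharged on oxygen, q the share of those patients with no CRF answer, and h the mean home-oxygen days. True oxygen days, q and h are taken as equal in both arms. The false difference in mean recorded days is d × q × h. All inputs are assumed.

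- Low: 0.05 × 0.25 × 7 = 0.09 days
- Middle: 0.10 × 0.50 × 14 = 0.7 days
- High: 0.20 × 1.00 × 21 = 4.2 days
- All CRFs answered: q = 0, so 0 days

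**4. Effect on the planned summary.** SAP 8.2.3 reports medians and quartiles, not means. In an illustrative simulation the true median was 7 days in both arms (lognormal, log SD 0.8, limited to 1 to 28 days). Half of the oxygen days were moved home for 15 to 30% of patients in one arm and 10% in the other. The medians differed by 0 or 1 day as q went from 0 to 100%. The means differed by 0 to 0.87 days.

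**The case against.** The strongest reply is that footnote 9 is being read too literally. Its restriction follows a bullet on vital signs, laboratory tests and samples. Appendix C 1.1 and 4.1 and SAP 4.1 describe remote visits as yielding clinical data without specimens. The clinical-data row of the schedule is marked on Days 15, 22 and 29, and footnote 2 says that it includes oxygen and ventilator requirement. Appendix C 8.1.2.1 lists oxygen requirement among the items recorded with the ordinal scale, and Appendix C 9.2 says that the components are captured separately. A CRF for post-discharge oxygen exists by name. It is not in the documents, and sites may well complete it at every contact.

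Much of this stands. It is wrong to say that remote contacts record nothing about oxygen, and the documents do not show that the CRF goes unanswered. But no protocol passage asks for the number of oxygen days since the last contact, and a one-day requirement cannot supply that number. The reply also leaves the SAP 6.5 gap and the 8.2.4 rule untouched.

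A reader might infer that oxygen moved home is generally counted as oxygen saved. The documents do not support that, because SAP 3.3.8 counts home oxygen whenever the CRF is answered. A reader might also multiply an assumed 15% of patients by 14 home days and report a mean shortfall of 2.1 days per patient. That treats every CRF as unanswered.

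**Conclusion.** The point holds in three parts.

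- Footnote 9 and SAP 3.3.6 to 3.3.8 disagree on what is collected at remote contacts.
- SAP 6.5 has no rule for a patient last seen on home oxygen. Under a score-only reading, a 28-day user can be counted as 7.
- SAP 8.2.4 contradicts the all-device definition in 3.3.8, whether or not the CRF is complete.

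The consequence is limited. These are additional secondary endpoints, and durations are summarised by medians and quartiles. They are not among the analyses whose p-values SAP 6.8 makes conditional on the primary result. The primary endpoint and the sample size are unaffected. The size of the loss in days is unknown: it is zero if the CRF is always answered, and the 0.09 to 4.2 day range for means rests wholly on assumed inputs.

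It may be tempting to say that the bias tracks any treatment effect on discharge. The documents give no basis for that. A difference between arms arises only if home-oxygen discharge or missing answers differ by arm, and neither is reported.

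**What to change.** 1. **Protocol Appendix C, footnote 9.** Add the existing Post-Discharge Supplemental Oxygen questions to the phone, telehealth and Day 22 items: days of oxygen, of non-invasive ventilation/high-flow and of invasive ventilation/ECMO since the last contact.
2. **SAP 6.5.** Treat a patient recorded as on new or increased home oxygen at the last assessment as on oxygen, using the separately captured oxygen item and not score 2 alone. Say also how unchanged pre-COVID home oxygen is handled, since Appendix C 8.1.2.1 allows such patients to score 1.
3. **SAP 8.2.4.** Let new oxygen use be identified from the CRF as well as from a score of at least 5, and apply the same definition in Table 33.

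The cost is a few questions on contacts that already take place, plus SAP wording. The drawback is that days at home rest on patient recall. For data already collected, reporting by arm how many discharged patients have the CRF completed would show how far SAP 6.5 matters.
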